1. INTRODUCTION

This statistical analysis plan (SAP) is for the pre-specified reporting of study results for protocol FGCL-3019-095, amendment 2.0. This SAP documents the planned analyses only for the open-label extension (OLE) period. Specifications of tables, data listings, and figures (TLF) are contained in a separate document. A separate SAP details the statistical analyses and methods for the double-blind period of FGCL-3019-095.

In this document, only new definitions and rules will be described. Cross reference to the double-blind SAP will be made for definitions and rules that will follow the same methodology used for the double-blind period of the trial.

2. STUDY OBJECTIVE

The overall objective of this Phase 3 registration-enabling study is to evaluate the efficacy and safety of 30 mg/kg intravenous (IV) infusions of pamrevlumab as compared to placebo in subjects with Idiopathic Pulmonary Fibrosis (IPF). The objective of the OLE phase is to evaluate the long-term safety of pamrevlumab in subjects with IPF, though efficacy assessments are included.

3. STUDY DESIGN (OLE PERIOD)

3.1. Enrollment to OLE Period

Subjects who complete the Week 48 visit of the main study (regardless of the number of study drug infusions received) will be eligible to participate in the optional, OLE period of the study. The OLE period offers continuing access to pamrevlumab regardless of randomization assignment (pamrevlumab or placebo) in double-blind period of the study. Subjects will be considered as having entered the OLE study if they have received at least one dose of the study drug during the OLE period.

3.2. Randomization

Randomization is not applicable for the OLE period.

3.3. Study Periods

- Optional, OLE period of pamrevlumab:
 - Access to pamrevlumab will be available until the last subject completes
 48 weeks of treatment in the OLE period, or pamrevlumab is commercially available for the indication of IPF, or the Sponsor decides to end the OLE period, whichever occurs first.
- Follow-up period/final safety assessments:
 - 28 days after the last dose
 - 60 days after the last dose: follow-up phone call, for a final safety assessment

4. STUDY ENDPOINTS (OLE)

The following efficacy and safety assessments will be collected only as standard-of-care per each investigational site's real-world practice and descriptively presented during the OLE period:

Efficacy assessments:

- Forced vital capacity (FVC) (L)
- FVC percent predicted (FVCpp)
- Absolute FVCpp decline of ≥10%
- All-cause mortality
- Change in high-resolution computed tomography (HRCT) Quantitative Lung Fibrosis (QLF) volume (if HRCT is performed as part of routine patient care)

Safety assessments:

Treatment-emergent adverse events (TEAEs) and treatment-emergent serious adverse events (TESAEs; including hypersensitivity/anaphylactic reactions) will be collected for 60 days after the last dose.

In addition, pre- and post-infusion vital signs and immunogenicity (Human Anti-Human Antibody [HAHA] formation) testing will be collected.

5. GENERAL STATISTICAL CONSIDERATIONS

5.1. Statistical Methodology

All data collected will be included in the data listings. All analyses will be performed using $SAS^{\text{@}}$ Version 9.3 or higher.

5.1.1. Analysis of Categorical Endpoints

Follow the same guidelines as described in SAP for the double-blind period.

5.1.2. Analysis of Continuous Endpoints

Follow the same guidelines as described in SAP for the double-blind period.

5.1.3. Analysis of Spirometry Data

Follow the same guidelines as described in SAP for the double-blind period.

5.1.4. Analysis of HRCT Data

Follow the same guidelines as described in SAP for the double-blind period.

5.2. Analysis Set

5.2.1. Safety Analysis Set - OLE

The **Safety Analysis Set - OLE (SAF-OLE)** includes all subjects who have received at least one study medication in the OLE period. Subjects will be analyzed according to the previous treatment actually received in the double-blind period.

All analysis in OLE will be performed on SAF-OLE unless otherwise specified.

5.2.2. Immunogenicity Analysis Set -OLE (IGS-OLE)

The IGS-OLE will include all subjects who are in SAF-OLE, have baseline antidrug antibody (ADA) assessment in the double-blind period, and have at least one evaluable ADA assessment in the OLE period.

5.3. General Data Handling Rules and Presentation Specifications

5.3.1. Analysis Period

• The primary analysis will be based on the on-study period which is defined as from Day 1 in the OLE period up to the end of the entire study, regardless of patients' treatment status.

5.3.2. Baseline Definitions

Baseline is defined as the last assessment prior to the first dosing in the OLE period with 2 exceptions below:

- Baseline in the double-blind period and OLE will be applied for assessments of FVC and QLF; and
- Baseline in the double-blind period will be applied for assessments of ADA.

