6.5. Treatments and Medications

6.5.1. Study Drug Exposure

Study treatment will be summarized for OLE period for SAF-OLE.

• Duration of exposure in the OLE period = date last non-zero dose in the OLE period – date of the first dose in the OLE period + 1.

Duration of study treatment in the OLE period will be summarized as a continuous variable and be tabulated by the categories as follows:

- <12 weeks
- 12 to <24 weeks
- 24 to <48 weeks
- 48 to <72 weeks
- 72 to <96 weeks
- >96 Weeks

Number of infusions is defined as the number of non-zero dose infusions.

The following dose administration parameters:

- Total number of infusions in the OLE period $(1-4, 5-8, 9-16, 17-24, 25-32, \ge 33)$
- Overall average infusion doses (in mg/kg) in the OLE period
- Whether infusion was interrupted and reason for interruption in the OLE period

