APPENDIX 1. ANALYSIS VISIT WINDOWS

Analysis visits are defined by the windows that will have the widths of the corresponding assessments centered at the scheduled time. Unscheduled visits within a visit window defined below will be grouped into the closest scheduled visits based on the visit date.

Table 1: Analysis Visit Window for Vital Signs

Analysis Visit	Target Day in OLE	Start Day	End Day
Baseline	See Sec	tion 5.3.2	
EX-Day 1 (postdose) [#]	1	1	1
EX-Week 3 (predose and postdose)	22	2	32
EX-Week 3*n (predose and postdose)	21*n+1	21*n-9	21*n+11
EX-28 Days post last dose [@]			**

^{**} end of OLE period

Table 2: Analysis Visit Window for PFT and Weight [#]

Analysis Visit	Target Day	Start Day	End Day
Baseline		See Section 5.3.2	
EX-Week 24	169	2	253
EX-Week 24*n [\$]	24*n+1	24*7*n-82	24*7*n+85

^[\$] n is 2, 3, 4, etc.

Note: The timing of PFT is dependent on local schedules.

Table 3: Analysis Visit Window for HRCT

Analysis Visit	Target Day	Start Day	End Day
Baseline		See Section 5.3.2	
EX-Week 24	169	2	253
EX-Week 24*n [\$]	24*n+1	24*7*n-82	24*7*n+85
EX-28 days Post last dose [@]			**

^{**} end of OLE period

Note: The timing of HRCT is dependent on local schedules.

^[\$] n is 2, 3, 4, etc.

^[@] Same as visit collected on CRF.

^[#] Weight baselines follow same rules as vital signs.

^[\$] n is 2, 3, 4, etc.

^[@] Same as visit collected on CRF.

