6.8.5. Vital Signs

Heart rate (beat/min), diastolic and systolic blood pressure (mmHg), temperature (°C), and body weight (kg) will be descriptively summarized by treatment at selected visits.

Vital sign values are potentially clinically significant (PCS) if they meet both the observed value criteria and the change from baseline criteria listed in Table 5 below. The number and percentage of subjects with post-baseline PCS values will be tabulated by treatment group. The percentages are to be calculated relative to the number of subjects with baseline and at least one post-baseline assessment. The numerator is the total number of subjects with at least one post-baseline PCS vital sign value. A supportive listing of subjects with post-baseline PCS values will be provided including the patient ID, study center, baseline, and post-baseline values. A listing of all AEs for subjects with PCS vital signs will also be provided.

Confidential Page 33 of 56

Wital Sian Danamatan	Ela a	Criteria*		
Vital Sign Parameter	Flag	Observed Value	Change from Baseline	
Systolic Blood Pressure (mmHg)	High	≥ 170	Increase of ≥ 20	
	Low	≤ 90	Decrease of ≥ 20	
Diastolic Blood Pressure (mmHg)	High	≥ 110	Increase of ≥ 15	
	Low	≤ 45	Decrease of ≥ 15	
Heart Rate (bpm)	High	≥ 120	Increase of ≥ 20	
	Low	≤ 50	Decrease of ≥ 20	
Weight (kg)	High	-	Increase of ≥ 10%	
	Low	-	Decrease of ≥ 10%	

Table 5: Criteria for Potentially Clinically Significant Vital Signs

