6.10.1. Terms and Definitions

6.10.1.1. Sample ADA Status

- Baseline ADA-positive sample: ADA is detected in the last sample before initiation of treatment
- Baseline ADA-negative sample: ADA is not detected in the last sample before initiation of treatment.
- **Treatment-emergent ADA-Positive**: Meets definition of treatment-induced or treatment-boosted ADA:
 - Treatment-induced ADA-Positive: a post-treatment positive ADA is detected in a subject for whom pre-treatment ADA assessment is either negative or not assessable
 - Treatment-boosted ADA-Positive: pre-existing ADA was boosted to a higher level following study treatment, i.e. pre-treatment positive ADA titer was boosted by at least 2 dilution steps (4-fold) following study treatment.
- **ADA-negative sample**: After initiation of treatment, ADA is not treatment-emergent ADA-positive.

Next, using the sample ADA status, the subject's ADA status is defined.

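### For ADA, vital signs and weight, the OLE SAP ties baseline to study period instead of first pamrevlumab dose, which suits only one of the two prior-treatment groups for each measure

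*SAP*

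**What the plan says.** The general rule in OLE SAP 5.3.2 is: "Baseline is defined as the last assessment prior to the first dosing in the OLE period with 2 exceptions below". The first exception gives FVC and QLF both a double-blind and an OLE baseline. The second reads: "Baseline in the double-blind period will be applied for assessments of ADA". Vital signs fall under the general rule, and a note to OLE SAP Appendix 1 adds: "Weight baselines follow same rules as vital signs". None of these rules depends on prior arm.

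OLE SAP 6.8 imports the ADA rules of the double-blind SAP. Section 6.10.1.1 of that document calls a sample treatment-induced when "a post-treatment positive ADA is detected in a subject for whom pre-treatment ADA assessment is either negative or not assessable". A subject already positive before treatment counts as treatment-emergent only after at least a 4-fold rise in titer.

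OLE SAP 6.7.2 imports the vital-sign rules. Under double-blind SAP 6.8.5, values are potentially clinically significant (PCS) "if they meet both the observed value criteria and the change from baseline criteria listed in Table 5 below". Weight is the exception: it is flagged on a change of at least 10% alone.

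OLE SAP section 2 gives the purpose: "The objective of the OLE phase is to evaluate the long-term safety of pamrevlumab in subjects with IPF".

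**The concern.** The OLE brings together subjects who have been on pamrevlumab since main-study Day 1 and subjects who first receive it on EX Day 1. A baseline fixed to one calendar point in the study cannot sit just before first exposure in both groups.

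For ADA, the double-blind baseline is right for the prior-pamrevlumab group. In the prior-placebo group it leaves the whole placebo year between baseline and first exposure, so antibodies that arise in that year can be attributed to the OLE treatment, which is pamrevlumab. For vital signs and weight the position is reversed: the OLE baseline is right for the prior-placebo group, but in the prior-pamrevlumab group it is an on-drug value.

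The OLE's main output is its safety tables. ADA incidence in the newly exposed group and cumulative change in the longest-exposed group both bear directly on the stated objective.

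**Working it through.** **Timing.** Main-phase dosing is Day 1 and every 3 weeks to Week 48 (Protocol synopsis): 48/3 + 1 = 17 infusions, which reproduces the protocol's stated maximum. EX Day 1 is 3 weeks ± 7 days after Week 48 (Protocol Appendix 6): 48 + 3 = week 51, range 50 to 52.

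**Trace of each baseline by prior arm.**

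| Measure | Prior arm | Baseline under OLE SAP 5.3.2 | Aligned with first pamrevlumab dose? |
|---|---|---|---|
| ADA | Pamrevlumab | Double-blind | Yes |
| ADA | Placebo | Double-blind | No: about 51 weeks too early |
| Vital signs, weight | Placebo | Last value before EX Day 1 | Yes |
| Vital signs, weight | Pamrevlumab | Last value before EX Day 1 | No: after up to 17 infusions |
| FVC, QLF | Both | Both | Covered |

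**ADA in a prior-placebo subject.**
- Negative on Day 1, positive at Week 48 on placebo, positive at the OLE sample with less than a 4-fold rise. From Day 1 this is treatment-induced. From Week 48 the subject is baseline-positive, not boosted, and so not treatment-emergent.
- Positive on Day 1, negative at Week 48, positive at the OLE sample with a titer less than 4-fold above Day 1. From Day 1 this is not treatment-emergent. From Week 48 it is treatment-induced. The error can therefore run in either direction.

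The text also leaves open which samples count. Double-blind SAP 6.10.1.2 makes a subject ADA-positive on any treatment-emergent sample during the study, whereas OLE SAP 5.3.1 starts the analysis period at OLE Day 1. Read literally, the first would count a placebo-phase positive even after it had cleared.

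**Weight in a prior-pamrevlumab subject** (constructed example: 80 kg at first dose, 75 kg at OLE baseline, 71 kg later).
- Double-blind report: (75 - 80)/80 = -6.3%, not flagged.
- OLE report: (71 - 75)/75 = -5.3%, not flagged.
- From first dose: (71 - 80)/80 = -11.3%, meets the 10% criterion.

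**Systolic pressure** (constructed example: 130, 108, 89 mmHg; the low flag needs a value of 90 or less and a fall of 20 or more).
- Double-blind report: the fall is 130 - 108 = 22, but 108 is above 90, so not flagged.
- OLE report: 89 is below 90, but 108 - 89 = 19, so not flagged.
- From first dose: 130 - 89 = 41 with a value of 89, so both criteria are met.

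**Is a later ADA baseline available?** Protocol Appendix 2 schedules HAHA on Day 1 and at Weeks 24, 36 and 48. The key changes for Amendment 2.0 (09 January 2023) show that Weeks 36 and 48 were added then, in a trial whose first protocol is dated 11 February 2020. The 28-day sample of an OLE entrant comes after the last OLE dose. A subject who passed Week 48 before the amendment took effect may therefore have nothing scheduled later than Week 24 before EX Day 1.

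**The case against.** The strongest reply is that little can go wrong. OLE SAP 5.3.4 makes all summaries descriptive and shows them by previous actual treatment as well as pooled. The double-blind report gives ADA incidence and prevalence by arm and lists every assessment, so placebo-phase positives can be seen there. OLE SAP 6.8 adds a detailed listing and rules out subgroup analysis by ADA status, so a misclassified subject does not affect other tables. The first 48 weeks on pamrevlumab are flagged against the double-blind baseline in the double-blind report. Since late samples were added only by Amendment 2.0, a uniform Day 1 baseline also has a practical rationale.

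Much of this stands. No test is affected, and a careful reader could rebuild the right answer from listings. But display by prior arm only locates the ADA error in the prior-placebo and pooled columns; it does not remove it. The two reports together still miss a change that reaches the threshold only across both periods. The plan already accepts the case for two baselines, since it uses them for FVC and QLF.

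A reader might also infer that the OLE exposure categories are wrong because they restart at zero for prior-pamrevlumab subjects. The documents do not support that. OLE SAP 6.5.1 defines the measure openly: "Duration of exposure in the OLE period = date last non-zero dose in the OLE period", less the first OLE dose date, plus one. Double-blind exposure is tabulated in its own report. A cumulative column would be an addition, not a correction.

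**Conclusion.** The point holds for ADA in prior-placebo subjects and for vital signs and weight in prior-pamrevlumab subjects. It should be corrected, but it is a matter of interpreting descriptive safety output and does not threaten any trial conclusion.

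The ADA size cannot be stated. It depends on how many placebo subjects turn positive and stay positive until the OLE sample, and the documents give neither rate. The vital-sign gap is limited to changes that meet the flag only cumulatively. The examples show that such changes are possible, not how common they are. The figure of 17 infusions is a maximum, because OLE entry does not depend on the number received.

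Three stronger readings go too far. One is that every OLE baseline is misaligned; FVC and QLF are not. Another is that first-year change in prior-pamrevlumab subjects is lost; the double-blind report covers it. The third is that a Week 48 antibody sample exists for every prior-placebo subject; the amendment history does not allow that assumption.

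**What to change.** In OLE SAP 5.3.2, define the ADA baseline as the last evaluable sample before the first pamrevlumab infusion. For prior-pamrevlumab subjects this is the double-blind baseline. For prior-placebo subjects it is Week 48 where collected, otherwise the latest earlier main-phase sample. Align the IGS-OLE definition in 5.2.2, which now requires a double-blind baseline assessment. State in 6.8 that only samples taken after the first pamrevlumab dose can count as treatment-emergent.

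For vital signs and weight in prior-pamrevlumab subjects, show change and PCS flags from both the double-blind and the OLE baseline.

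The cost is SAP wording, programming and one extra display; no new sample or measurement is needed. The drawback is mixed timing of the ADA baseline among prior-placebo subjects. A count of subjects by the visit that supplied the baseline would make this visible.

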5.3.3. Formulas

- Study Day Calculation
 - The day when a subject receives the first dose of study drug in the OLE period is designated as Day 1 in OLE.
 - Study day of an assessment/procedure is calculated as follows.
 - For assessments or procedures on Day 1 or later, Study day = assessment/procedure date - Day 1 date + 1.
 - For assessments or procedures earlier than Day 1, Study day = assessment/procedure date - Day 1 date.
- Follow the same formulas as described in SAP for the double-blind period:
 - Body Mass Index (BMI)
 - Body weight, height, and temperature
 - (Absolute) Change from Baseline

- Relative change from baseline (%)
- Patient exposure years (PEY) (on pamrevlumab in OLE period):
 - PEY = Number of subjects × Average Duration of Exposure, where duration of exposure is (date of last non-zero dose on pamrevlumab date of first dose in OLE period on pamrevlumab + 1)/365.25.

5.3.4. General Instructions of TLF

Follow the same guidelines as described in SAP for the double-blind period.

Summary tables will be presented for each previous actual treatment group in the double-blind period and all subjects pooled in the OLE period.

Efficacy and safety data will be summarized descriptively for subjects who entered OLE. No formal statistical inference will be performed.

5.3.5. Handling Dropouts and Missing Data

For handling of dropouts and missing data the same guidelines will be followed as described in SAP for the double-blind period. No imputations will be performed on post-death analysis visits.

5.4. Interim Analysis and Data Monitoring Committee

In addition to routine safety monitoring, an independent Data Monitoring Committee (DMC) will be established to review safety data on an ongoing basis. A DMC charter will establish the procedures, meeting frequency, and scope of responsibilities of the committee.

This study has no planned or pre-specified interim analysis for either efficacy or futility.

6. STATISTICAL ANALYSIS

6.1. Subject Accountability and Disposition

The number (%) of subjects who entered the OLE period, discontinued prematurely from treatment, discontinued prematurely from study, and reasons for premature discontinuation will be presented for each previous treatment group in the double-blind period and all subjects pooled.

Enrollment will also be summarized by study site.

6.2. Protocol Deviations

The number and percentage of subjects with important protocol deviations will be categorized and tabulated as appropriate. COVID-19 related important protocol deviations will be summarized in a separate table. All protocol deviations will be finalized prior to the OLE database lock.

6.3. Demographics

Demographic summaries will follow the same guidelines as described in SAP for the double-blind period.

6.4. Concomitant Medications

Concomitant medications summaries will follow the same guidelines as described in SAP for the double-blind period.

6.5. Treatments and Medications

6.5.1. Study Drug Exposure

Study treatment will be summarized for OLE period for SAF-OLE.

• Duration of exposure in the OLE period = date last non-zero dose in the OLE period – date of the first dose in the OLE period + 1.

Duration of study treatment in the OLE period will be summarized as a continuous variable and be tabulated by the categories as follows:

- <12 weeks
- 12 to <24 weeks
- 24 to <48 weeks
- 48 to <72 weeks
- 72 to <96 weeks
- >96 Weeks

Number of infusions is defined as the number of non-zero dose infusions.

The following dose administration parameters:

- Total number of infusions in the OLE period $(1-4, 5-8, 9-16, 17-24, 25-32, \ge 33)$
- Overall average infusion doses (in mg/kg) in the OLE period
- Whether infusion was interrupted and reason for interruption in the OLE period

6.5.2. Treatment Compliance

Follow the same guidelines as described in SAP for the double-blind period.

6.6. Efficacy Analysis

All analyses for efficacy endpoints will be performed for the SAF-OLE during the on-study period unless noted otherwise.

6.6.1. Efficacy Endpoint Analysis and Estimand

6.6.1.1. Estimand Strategy

The primary estimand is intended to provide a population-level assessment of the pamrevlumab on a continuous endpoint, regardless of participant compliance with the IP dosing.

6.6.1.2. Population of Interest

All subjects in SAF-OLE.

6.6.1.3. Intercurrent Event Handling Strategy

Treatment policy strategy will be used for any intercurrent event. No imputation on missing data.

6.6.1.4. Analysis Variable

Follow guidelines in SAP for the double-blind period.

6.6.1.5. Population Summary

Efficacy parameters, including change from baseline in FVC (L), FVCpp, and HRCT fibrosis score will be summarized descriptively at each scheduled visit as defined in Appendix 1.

6.7. Safety Analysis

The safety analyses will be performed for the SAF-OLE in the OLE period.

6.7.1. Adverse Events (AEs)

Follow the same guidelines as described in SAP for the double-blind period with additional PEY for OLE period on pamrevlumab will be provided.

6.7.2. Vital Signs

Follow the same guidelines as described in SAP for the double-blind period. The analysis visit window is defined in Appendix 1.

6.8. ADA Analysis

ADA analyses follow the same guidelines as described in SAP Part 1 for the double-blind period.

Considering ADA assessment was collected only on 28 days after last dose in the OLE period, ADA incidence will be summarized on IGS-OLE. A listing with details will be provided for SAF-OLE.

No subgroup analysis will be performed by ADA status.

6.9. PK Analysis

Not applicable for the OLE period.

7. CHANGES FROM PROTOCOL

Respiratory hospitalization and acute IPF exacerbation endpoints have been removed in this 095 OLE SAP, as adjudication of these events was only performed for the double-blind period of the study.

